3.0 TREATMENT PLAN

3.1 Schema

After initial evaluation for eligibility and signing of the informed consent, fiducial markers will be placed via percutaneous approach by interventional radiology.

CT scans will be obtained, and when necessary, CT scans will be registered with MRI scans. The gross tumor volume (GTV) as well as the location of the GTV will be defined based on placement of the fiducial markers. The fiducial placement will be carried out by interventional radiology. For treatment planning, the GTV will be expanded by 5 mm in all directions except for supero-inferior where the expansion will be 8 mm. This expansion will account for both clinical target volume (CTV) expansion and motion. Treatment planning software will be used to plan radiation delivery schemes that will best meet the dose criteria defined above. The prescription dose will be modified as necessary as per section 3.3 to meet the defined liver tolerance dose.

Because of the difference in anatomy and expected normal tissue tolerance based on hepatic function, there are two well defined patient cohorts. The first cohort comprises of patients with good liver functions and peripheral lesions. The second cohort is comprised of patients with Child-Pugh Class B lesions where liver tolerance is more likely to be a problem.

Treatments will be delivered with standard CyberKnife procedures and the Synchrony™ option to account for respiratory motion and set up variations. The fiducial location will be the prime determinant of the delivery site and respiratory motion.

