A radiosurgical treatment plan will be developed based on tumor geometry and proximity to vital structures. The treating surgeon and or the treating radiation oncologist will contour the tumor as well as all dose-limiting structures. Briefly, the lesion representing the gross tumor volume (GTV) will be outlined on sequential axial computed tomography images utilizing soft tissue/liver windowing. Planning target volume (PTV) is created by expanding GTV by 0.5-0.8 cm in all directions. The dose will be prescribed to the minimal isodose line that covers (>95%) the PTV. All vital structures close to the irradiated target, potentially including the heart, esophagus, aorta, spinal cord, and stomach will be contoured for the purpose of limiting incidental radiation to these structures and for the development of dose volume histograms (DVH).

The Stereotactic Radiosurgical Procedure

The CyberKnife (CK) treatment will generally be initiated within 1 to 2 weeks of the planning treatment CT. On the day of CK treatment, the subject will be taken into the CK treatment room and the applicable LED (light emitting diode) monitors will be attached. The LEDs will assist the system to track the tumor throughout the respiratory cycle. The subject then will be set up in their immobilization cradle on the CyberKnife couch. X-rays will be taken with the CyberKnife System to ensure that the tumor is aligned in a manner consistent with the position in which the treatment plan CT image was taken. Fiducial locations in the images will be extracted and compared to the fiducial locations in the CT scans to estimate tumor movements. Once the tumor is properly aligned, SRS will be initiated. During the course of SRS, x-rays will continue to be taken periodically to ensure correct tumor alignment. The SRS treatment will be administered in three to five fractions, given over 3-15 days.

First Cohort (good liver function):

The planned initial dose to all patients with peripheral lesions and no more than Child-Pugh Class A will be 1500 cGy delivered to the prescription point for 3 fractions for a total of 4500 cGy if the dose-normal tissue constraints as defined below can be met. Treatments are delivered

≥ 48 hrs apart and should be completed within 2 weeks depending on routine scheduling or maintenance related issues with the CyberKnife. No treatment should be completed in less than 5 days (i.e., M, W, F is most common).

Second Cohort (compromised liver function):

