2). The secondary study end-point will be local tumor response and control. Our expectation is that a dose of 1500 cGy per fraction for 3 fractions (4500 cGy total) will be adequate for control of irradiated lesions of moderate size, but higher doses may be needed. In the second cohort the optimal dose is less clear, and dose escalation will likely be desired. Patients will be evaluated for local control at 5-6 months after irradiation. A minimum of 10 patients will be entered onto each dose cohort. However, if there are 4 local failures within a cohort at dose level 1 dose escalation may proceed provided the tolerance parameters are acceptable (that is, conditions in both Tables 5A and 5B are satisfied), and patients have been evaluated for toxicity for at least 3 months from the initiation of therapy. At that point, dose escalation to a nominal prescription dose per fraction of 1750 cGy in the first cohort, and 850 cGy in the second cohort, will be undertaken. A second dose escalation with the same increase in dose/fraction could occur based on the same parameters as above. Escalation of the two cohorts will be done separately as their tolerance might be different. No intra-patient dose escalation will be allowed. For dose escalation, if the proposed dose for escalation is found to be too toxic, based on Tables 3 and 4, the study will be stopped. All patients in a cohort will be followed for 3 months from the time of initiation of therapy for evaluation of toxicity, prior to dose escalation in each cohort.

Table 5A

# of patients with a DLT	Total # patients in cohort	Action
0	5, 6, 7, 8	DLT rate warrants escalation to next dose level for subsequent patients ¹
≤ 1	9, 10	DLT rate warrants escalation to next dose level for subsequent patients ¹

¹ Dose escalation will only occur in patients eligible for full dose, see text of protocol

Table 5B

# of patients with unexpected Grade 3 ¹	# of patients with unexpected Grade 4	Total # patients in cohort	Action
≤ 1	0	5, 6, 7, 8	Rate of unexpected toxicities warrants escalation
≤ 2	0	9, 10	Rate of unexpected toxicities warrants escalation
≤ 0	1		

¹ A patient with both unexpected Grade 3 and Grade 4 toxicities is counted as a patient with unexpected Grade 4 toxicity

To summarize, the goal is to find a dose such that:

- 1). The rate of dose limiting hepatic toxicity at that dose does not exceed 0.33.
- 2). The rate of unexpected Grade 3 plus double the rate of Grade 4 toxicities does not exceed 0.4.;

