5.6 Assessment of Disease Status

Criteria for response evaluation in patients with measurable disease:

Patients eligible for this trial must have at least one measurable liver lesion and no more than 3 liver lesions. Any of these measurable liver lesions irradiated under this protocol will be separately evaluated for progression/response. These measurable irradiated lesions must be accurately measured in at least two dimensions.

Progression in any non-irradiated liver lesion or distant site (including non-measurable disease e.g., ascites, malignant pleural/pericardial effusion, bone lesions, or marrow involvement) will be evaluated separately. These non-irradiated lesions will be followed up for progression only.

It is a known and expected effect from radiosurgery for there to be peri-lesional enhancement up to 2.5 cm surrounding the target lesion that will not be considered as part of the response criteria or as tumor progression. Therefore, specifically for the irradiated liver lesions, the 8 weeks post treatment tumor assessment will be considered baseline for evaluation of progression/response.

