5.6.1 Response evaluation (Evaluation of Irradiated Liver Lesions)

Complete Response (CR): Disappearance of all target lesions. Lack of any PET activity will also be measured as an indicator of response, but will not be used in the formal evaluation of CR.

Partial Response (PR): Regression of measurable disease and no new sites.

Stable Disease (SD): Does not qualify for CR or PR, and does not fulfill criteria for progressive disease.

Progressive Disease (PD): Increase by $\geq 50\%$ in the product of two perpendicular diameters of a previously irradiated lesion

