5.6.2 Evaluation of Progression in non-irradiated Lesions

Progressive Disease: The appearance of one or more new lesion(s) and/or unequivocal progression of existing non-irradiated lesions. If there is any question regarding whether a non-irradiated lesion meets the criteria for progression, please check with the study PI, [name].

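### The response rules give a discrete in-field or marginal recurrence no route to local failure, so local control can be overstated

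*Combined protocol and SAP*

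**What the plan says.** **Response rules.** Section 5.6 treats as an expected effect of radiosurgery "peri-lesional enhancement up to 2.5 cm surrounding the target lesion that will not be considered as part of the response criteria or as tumor progression". From this it concludes that, for irradiated liver lesions, "the 8 weeks post treatment tumor assessment will be considered baseline for evaluation of progression/response". Section 5.6.1 makes an irradiated lesion progressive when there is a rise of 50% or more "in the product of two perpendicular diameters of a previously irradiated lesion", and gives no other criterion. Partial response is "Regression of measurable disease and no new sites", so a new site blocks PR. The CR and PD definitions in 5.6.1 do not mention new lesions. Section 5.6.2, which is headed as covering non-irradiated lesions, defines progression as "The appearance of one or more new lesion(s) and/or unequivocal progression of existing non-irradiated lesions". It makes no exception for a lesion close to the target. Its referral to the principal investigator concerns whether a non-irradiated lesion has progressed, not whether a lesion lies in the treated field.

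**Treated margin.** Section 3.1 says "the GTV will be expanded by 5 mm in all directions except for supero-inferior where the expansion will be 8 mm". Section 3.2 says "Planning target volume (PTV) is created by expanding GTV by 0.5-0.8 cm in all directions".

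**Use of the endpoint.** Sections 3.2 and 7.1 say "Patients will be evaluated for local control at 5-6 months after irradiation". Four local failures at dose level 1 allow escalation if the toxicity conditions of Tables 5A and 5B are met. One of the three summary goals is a local control rate of at least 70%. Section 7.2 describes the same trigger as a local failure rate above 30%. Neither local failure nor local control is defined anywhere in the document.

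**The concern.** Recurrence inside the treated volume or at its edge is the most direct evidence that the dose or margin did not control the tumour. It should be the core of a local-control endpoint. Under the rules as written, a separate nodule of this kind adds nothing to the target's diameter product and matches the new-lesion wording of 5.6.2. If the target itself has vanished, it still meets CR. If it has only shrunk, the new site removes PR and leaves stable disease. Neither is progression of an irradiated lesion.

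Contiguous regrowth is a second, weaker route to a missed failure. It lies within the 2.5 cm in which enhancement is set aside, and the reader has no stated way to tell the two apart.

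The error runs in one direction: failures are missed, so apparent control rises. With 10 patients per level, one missed failure out of four is enough to meet the 70% goal and keep the trigger from firing.

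**Working it through.** **1. The plan's own figure.** The smallest k with k/10 > 0.30 is 4, since 3/10 is exactly 30%. The 4-failure trigger therefore agrees with the above-30% description in Section 7.2. If 4 patients truly fail and 1 of them is not counted, the record shows 3 failures and 7/10 = 70% control. The goal is met and the trigger is not.

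**2. Where the treated edge lies.** The margin is 5 to 8 mm and the enhancement zone reaches 25 mm. The PTV edge is therefore 25 − 8 = 17 mm to 25 − 5 = 20 mm inside the zone.

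**3. What the 50% rule captures.** For a round lesion of diameter d, the product ratio is (new diameter 1 × new diameter 2)/d², and PD needs at least 1.5. Equal growth in both diameters must reach √1.5 = 1.225, that is 22.5%. The documents give no lesion sizes, so the diameters below are assumptions.

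| Assumed d | 5 mm on all sides | 8 mm per side in one axis, 5 mm in the other | One-sided growth of 5 mm | One-sided growth of 8 mm |
|---|---|---|---|---|
| 20 mm | 2.25 | 2.70 | 1.25 | 1.40 |
| 30 mm | 1.78 | 2.04 | 1.17 | 1.27 |
| 50 mm | 1.44 | 1.58 | 1.10 | 1.16 |

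For example, at 30 mm: (40/30)² = 1.78 and (46 × 40)/30² = 2.04. One-sided growth of 5 mm gives 35/30 = 1.17.

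Contiguous regrowth around the whole lesion can therefore reach PD while still inside the 2.5 cm zone. One-sided growth to the margin does not reach it at these sizes. A discrete nodule leaves the product unchanged (ratio 1.0) at any size.

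**4. Effect on the trigger.** Let p be the true local failure rate and f the share of failures that are marginal and uncounted. Both are assumptions. The counted rate is q = p(1 − f), and P(at least 4 of 10 counted) = 1 − Σ C(10,k) q^k (1 − q)^(10−k), summed over k = 0 to 3.

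| p | f = 0 | f = 25% | f = 33% | f = 50% |
|---|---|---|---|---|
| 30% | 0.350 | 0.169 | 0.121 | 0.050 |
| 40% | 0.618 | 0.350 | 0.264 | 0.121 |
| 50% | 0.828 | 0.553 | 0.441 | 0.224 |

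At p = 40% and f = 25%, q = 0.40 × 0.75 = 0.30, so expected apparent control is 70% against a true 60%. At f = 50%, q = 0.20 and apparent control is 80%.

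**5. Timing of the scans.** Week 20 is about 4.6 months after treatment. The next scheduled scan is three months later, at about 7.6 months. The Week 20 scan is thus the last scheduled one before the 5-6 month evaluation closes.

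**The case against.** A reader might infer that an edge recurrence can never be a local failure, or that nothing within 2.5 cm of the target is ever progression. The documents do not support that, for three reasons.

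- Section 5.6 sets aside enhancement expected from radiosurgery, not tumour or mass. It ties the point to the 8-week re-baseline, which suggests that early post-treatment change is meant.
- Section 5.6.1 has no distance limit, so contiguous regrowth measured as the lesion counts once it reaches 50%. The shortfall for one-sided growth comes from that threshold, not from the 2.5 cm sentence.
- Local failure is undefined. Marginal recurrence is left without a rule rather than expressly ruled out, and it can be argued that a nodule inside the PTV is not a non-irradiated lesion.

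It is also fair to say that the trigger only permits escalation, that local control is a secondary and preliminary objective, and that under Section 5.5 progression confined to non-irradiated lesions does not end follow-up. The volume of the 2.5 cm zone is no measure of harm, because it bounds where enhancement may appear and not where tumour goes uncounted.

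These points limit the claim about contiguous regrowth and its consequences. They do not close the gap for a discrete nodule: the only category that names new lesions is 5.6.2. The re-baseline does not help with a nodule first seen at Week 20, and continued follow-up captures later growth of the target, not the nodule.

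**Conclusion.** The concern holds in a limited form. By the stated rules, a discrete new nodule within or abutting the PTV has no route to progression of an irradiated lesion and would be filed under non-irradiated progression. Some contiguous regrowth could also be read as expected enhancement, because that exclusion has neither a time limit nor a criterion. Local failure can therefore be undercounted, and local control overstated, against the 70% goal and the 4-failure trigger.

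The direction is clear but the size is not. The probabilities are illustrations that rest on an assumed true failure rate, an assumed marginal share, 10 evaluable patients who fail independently, and every marginal failure going uncounted. If discrete marginal recurrence is rare, the effect is small. The case for a change is that the count feeds a decision rule in which one patient matters.

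**What to change.** 1. In 5.6.1, define local failure as either (a) PD of the irradiated lesion by the existing 50% rule, or (b) a new nodular or mass-like lesion within or abutting the PTV contour on CT or MRI after the 8-week baseline.
2. Limit 5.6.2 to lesions clear of the PTV.
3. State in 5.6 that the exclusion covers expected enhancement without a new mass.
4. For cases still uncertain at the 5-6 month evaluation, report local control both ways, with these cases counted and not counted as failures, and update when the next scheduled scan is read. Waiting for that scan, at about 7.6 months, would delay the count. The protocol should also say in advance which of the two counts feeds the 4-failure rule.

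The cost is protocol wording and reading effort. The planning contours and scheduled scans already exist, and no treatment or visit changes. The reader must compare follow-up scans with the planning contours, and reported local control may be slightly lower.

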5.6.1 Response evaluation (Evaluation of Irradiated Liver Lesions)

Complete Response (CR): Disappearance of all target lesions. Lack of any PET activity will also be measured as an indicator of response, but will not be used in the formal evaluation of CR.

Partial Response (PR): Regression of measurable disease and no new sites.

Stable Disease (SD): Does not qualify for CR or PR, and does not fulfill criteria for progressive disease.

Progressive Disease (PD): Increase by $\geq 50\%$ in the product of two perpendicular diameters of a previously irradiated lesion

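### The partial-response rule for irradiated lesions (5.6.1) has no minimum decrease and an unlimited no-new-sites condition, so the PR/SD split does not measure local response cleanly

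*Combined protocol and SAP*

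**What the plan says.** Section 5.6.1, which covers irradiated liver lesions, lists four categories:

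- CR: "Complete Response (CR): Disappearance of all target lesions". There is no condition about new disease.
- PR: "Partial Response (PR): Regression of measurable disease and no new sites". There is no percentage, unit or location.
- SD is what is left over: "Does not qualify for CR or PR, and does not fulfill criteria for progressive disease".
- PD: an increase of at least 50% "in the product of two perpendicular diameters of a previously irradiated lesion".

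Section 5.6 sets the frame. Of irradiated lesions it says "Any of these measurable liver lesions irradiated under this protocol will be separately evaluated for progression/response". Of all other disease it says "These non-irradiated lesions will be followed up for progression only". The reference scan for irradiated lesions is fixed: "the 8 weeks post treatment tumor assessment will be considered baseline for evaluation of progression/response". The stated reason is peri-lesional enhancement after radiosurgery.

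Section 5.6.2 already has a place for new disease. Its definition of progression in non-irradiated lesions is "The appearance of one or more new lesion(s) and/or unequivocal progression of existing non-irradiated lesions".

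Local response is named, together with local control, in the secondary objective (2.2) and the secondary endpoint (3.2 and 7.1). Section 7.3 refers back to 7.1 and adds no response definition.

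**The concern.** The PR rule has two faults, and they push the reported rate in opposite directions.

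(a) PD needs a 50% change in the product, but PR needs only regression of unstated size. Lesions must be measured in two dimensions, so a PR threshold on the same scale was available. Without one, measurement error alone can move a lesion from SD to PR.

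(b) The new-sites condition is not limited to the treated lesions. A patient whose irradiated lesion shrinks while a new lesion appears elsewhere fails PR, does not meet the irradiated-lesion PD rule, and so falls to SD. A true local response is then reported as none.

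At stake is the local response rate, within dose levels of 10 patients (Table 2). A reader of the results could not tell how much of an observed PR count came from error, or how many local responses the new-sites condition had hidden.

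**Working it through.** The documents give no response rate, target or sample size that depends on PR, so there is no stated figure to reproduce. The check has a text part and an illustrative calculation.

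**Text, part (b).** Take a shrinking irradiated lesion with a new lesion elsewhere.

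- 5.6.1: not CR, not PR (new site), not PD (no 50% increase), hence SD.
- 5.6: irradiated lesions are judged on their own, and other disease is judged separately for progression only.
- 5.6.2: the new lesion is already PD of non-irradiated disease.
- 5.5: follow-up continues after progression confined to non-irradiated disease, so irradiated lesions are still being assessed.
- CR in the same list has no such condition.

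The SD result conflicts with the other four provisions. The case is foreseeable: 4.1 admits patients with extrahepatic metastases, and liver imaging is scheduled at Weeks 8 and 20 and then every three months (5.1).

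**Size of (b).** If r is the true local PR rate and q the share of those patients with a new site at the scored scan, the counted PR rate is r × (1 − q). The documents give neither value. Assuming r = 50%, q of 10%, 20% and 30% gives 45%, 40% and 35%.

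**Size of (a), inputs (all assumed).** A lesion truly unchanged after Week 8; true diameters of 15, 30 or 50 mm; log-normal error with CV 5%, 10% or 15% per diameter; one later scan compared with Week 8. The two diameter errors within a scan are either independent or fully correlated.

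*No cut-off.* With continuous measurement, P(later product < Week 8 product) = 0.50. Rounding to 1 mm produces ties and lowers this. Simulation of 400,000 lesions per setting gives 0.41-0.50 (independent) and 0.32-0.48 (correlated). The lowest values are at 15 mm with CV 5%, the highest at 50 mm with CV 15%.

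*With a cut-off c.* P(false PR) = Φ(ln(1 − c)/SD), where SD of the log product ratio is 2 × CV (independent) or 2√2 × CV (correlated).

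| Errors | CV | SD | c = 25% | c = 50% |
|---|---|---|---|---|
| Independent | 5% | 0.100 | 0.2% | <0.01% |
| Independent | 10% | 0.200 | 7.5% | 0.03% |
| Independent | 15% | 0.300 | 16.9% | 1.0% |
| Correlated | 5% | 0.141 | 2.1% | <0.01% |
| Correlated | 10% | 0.283 | 15.5% | 0.7% |
| Correlated | 15% | 0.424 | 24.9% | 5.1% |

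With 1 mm rounding at 15 mm, the largest 50% cut-off value becomes 5.6%.

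*Cost of a cut-off.* For a lesion whose product truly falls 30% after Week 8, P(PR) = Φ((ln(1 − c) − ln 0.7)/SD) over CV 5-15%:

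- No cut-off: 88-100% (independent), 80-99% (correlated).
- c = 25%: 59-75% and 56-69%.
- c = 50%: 0.04-13% and 0.9-21%.

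*Baseline.* A lesion that shrank 60% by Week 8 and then held is unchanged from Week 8, so a 50% cut-off calls it PR in at most 5.1% of cases (the c = 50% column). Against the pre-study scan, Φ(ln(0.5/0.4)/SD) gives 77-99% (independent) and 70-94% (correlated).

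**The case against.** The strongest reply is that nothing in the design turns on PR. The aim in 2.2 is preliminary data, the efficacy goal is local control of at least 70%, and escalation responds to local failures. This stands, and it limits the consequence to a descriptive endpoint. A reader might infer that dose escalation is compromised, but the documents do not support that: neither fault moves a lesion into or out of PD. The reservation is that the protocol never says local failure is PD under 5.6.1.

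Second, a reader might multiply 32-50% by 10 patients and expect 3 to 5 false PRs per dose level. That requires every lesion to be truly unchanged after Week 8 and every 1 mm fall to be called regression. Assessors may well not do that, so the figure bounds the literal rule and does not forecast results.

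Third, the 5.6.1 heading and the separation in 5.6 might lead an assessor to ignore lesions elsewhere. That reading is possible, but the clause does not state it, and two sites could score the same scans differently.

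Fourth, any cut-off brings its own misclassification. This is correct: a 50% rule from Week 8 misses most true 30% regressions. It argues for a deliberate choice of cut-off and for reporting the continuous change, not for leaving the rule open.

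A reader might also extend the point to PD, for instance to a lesion that vanishes and returns. That is a separate matter. It could affect failure counts and the end of follow-up, and it is not part of the PR/SD problem.

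**Conclusion.** The concern holds for the PR/SD split. Taken literally, the rule lets error create PRs (about 32-50% of unchanged lesions at one scan, under the assumed CVs and sizes and as an upper-end illustration). It also lets disease elsewhere remove true local PRs, by a proportion q that the documents do not give. The contradiction in (b) rests on the text alone and needs no assumption.

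It would go too far to say that the split does not measure local response at all. A clear regression without new sites is still a valid PR, and CR is untouched. PD counts and the hepatic toxicity endpoint are also unaffected. The 70% goal and the four-failure trigger are unaffected if local failure means PD under 5.6.1. The change should be made, but it does not bear on the trial's decision rules as far as the documents define them.

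**What to change.** 1. Delete the new-sites condition from the irradiated-lesion PR, and report new lesions only under 5.6.2.
2. State a minimum decrease for PR in the bidimensional product from the Week 8 baseline, the scale already used for PD. The sponsor should choose the value knowing the trade-off. A 50% cut-off (mirroring the PD figure) holds false PRs to at most about 5-6% under these assumptions, but misses most true 30% regressions. A 25% cut-off gives about 0.2-17% false PRs with independent errors and 2-25% with fully correlated errors, and detects more moderate regressions.
3. Report the continuous percentage change in the product from Week 8, so that the result does not rest on the cut-off alone.
4. Keep Week 8 as the primary baseline and add change from the pre-study scan as a sensitivity analysis, because no cut-off from Week 8 can credit earlier shrinkage. State beside it that peri-lesional enhancement is the protocol's reason for the Week 8 baseline, and that the pre-study scan may be up to 8 weeks before treatment (5.1, footnote a) and so may include growth before radiation.

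Cost: a wording amendment to 5.6.1 that goes to the sites' IRBs (8.7), with no new scans. The cut-off will lower the reported PR rate, while deleting the new-sites condition may restore some PRs.

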5.0 EVALUATIONS AND ASSESSMENTS

5.1. Time and Events Table

Assessments	Pre-Study ^a	Cyberknife RT Delivery ^b	Post RT Week 1 ^h	Post RT Week 4	Post RT Week 8	Post RT Week 20	Follow-up q 3 Months ^c x 2 Years
Informed Consent	X						
History and PE	X	X		X	X	X	X
Performance Status	X			X	X	X	X
Chest x-ray	X						
CBC	X		X	X	X	X	
Liver function tests (T Bili, INR, PT for Child-Pugh score, AST, ALT, LDH, Alk Phosphatase, Albumin)		X		X	X	X	X
Serum Creatinine	X						
Circulating Tumor Markers : AFP (HCC) or CEA (CRC)	X				X	X	X
CT and/or MRI of liver, PET scan is optional	X				X	X	X
Fiducial Placement ^d	X						
Liver Biopsy (if needed for diagnosis confirmation)	X ^g						
Treatment Planning ^e	X						
Toxicity Assessment		X	X	X	X	X	X
Pregnancy Test	X ^g						

^a Pre-study assessments to be completed within 8 weeks prior to start of Cyberknife Radiation Therapy Treatment.

^bCyberKnife radiation therapy (RT) will be completed within 2 weeks depending on routine scheduling or maintenance related issues with the CyberKnife. No treatment should be completed in less than 5 days.

^c Every three months following week 20. See section 5.5 for additional details.

^dThis would be done after study entry but prior to radiation therapy (RT).

^eTo be done at least 6 days following fiducials placement. Participants will be immobilized using Vac-Loc and Synchrony vest to facilitate in obtaining the treatment planning CT.

^g Within 14 days pre-study, and only if clinically appropriate

^h Patients in whom high dose irradiation is delivered to the main hepatic ducts or common bile duct will be considered for elective stent placement within the first 4 weeks after completion of radiation therapy to prevent biliary obstruction.

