5.4 Post-treatment Assessments (Up to week 20 after RT Treatment)

- History and physical examination
- Performance status
- Laboratory studies including CBC, and liver function tests
- CT, PET or MRI of the liver will be performed at, 8 and 20 weeks after the completion of radiation therapy and then at regular intervals per Section 5.1.
- Toxicity assessment (NOTE: this should occur up to week 20 regardless of whether disease recurs prior to this point or not).

5.5 Follow-up Assessments:

Follow-up will be done every three months for two years, or until disease progresses in an irradiated liver lesion. If disease progresses in a non-irradiated lesion only, follow-up will continue until disease progresses in one of the irradiated liver lesions. Once disease progresses in an irradiated liver lesion, protocol follow-up will cease other than follow-up of any unresolved treatment-related toxicity. Follow-up assessments will include:

- History and physical examination
- Performance status
- Laboratory studies for liver function tests
- CT, PET or MRI of the liver.
- Toxicity assessment

Patients in whom high dose irradiation is delivered to the main hepatic ducts or common bile duct will be considered for elective stent placement within the first 4 weeks after completion of radiation therapy to prevent biliary obstruction.

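### Progression of an irradiated lesion is judged only against the week-8 scan, so regrowth after later shrinkage is not progression until 1.5 times the week-8 product, and is undefined for a lesion already gone at week 8

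*Combined protocol and SAP*

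**What the plan says.** - **Progression (5.6.1):** an increase of 50% or more "in the product of two perpendicular diameters of a previously irradiated lesion". That sentence names no comparator.
- **Comparator (5.6):** for irradiated lesions, "the 8 weeks post treatment tumor assessment will be considered baseline for evaluation of progression/response". The reason given is that enhancement of up to 2.5 cm around the target is expected after radiosurgery and should not count as growth.
- **Other categories (5.6.1):** "Complete Response (CR): Disappearance of all target lesions"; "Partial Response (PR): Regression of measurable disease and no new sites", with no percentage. Stable disease is whatever fits none of the others.
- **Appearance of lesions (5.6.2):** "The appearance of one or more new lesion(s) and/or unequivocal progression of existing non-irradiated lesions". This applies only to non-irradiated lesions. No rule covers an irradiated lesion that returns.
- **Scans:** imaging "will be performed at, 8 and 20 weeks after the completion of radiation therapy" (5.4), then "Every three months following week 20" (footnote c to the table in 5.1).
- **End of follow-up (5.5):** "Once disease progresses in an irradiated liver lesion, protocol follow-up will cease other than follow-up of any unresolved treatment-related toxicity".
- **Use of local control (3.2, 7.1, 7.2):** patients are evaluated at 5-6 months. Four local failures in a cohort at dose level 1 can open escalation if the tolerance conditions are met. The dose sought must give at least 70% local control. Neither the four failures nor the 70% has a stated time limit, and local failure and local control are not defined by the 5.6.1 categories.

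**The concern.** With one fixed reference, the growth needed to call progression depends on how far the lesion has shrunk since that scan. The deeper the later response, the more regrowth is tolerated before the lesion changes category. Until then it is recorded as partial response or stable disease.

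Moving the fixed scan would not help, because any single reference fails in the same way once a lesion falls below it.

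Three things are at stake: the recording of late local failures, the progression date that ends protocol follow-up, and any late failures counted toward the 70% goal or the four-failure trigger.

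**Working it through.** **1. The plan's own figure.** Section 7.2 gives 10 patients per dose level and a local failure rate above 30%. Three of 10 is 30% and does not exceed it; four of 10 is 40% and does. The four-failure trigger in 3.2 and 7.1 reproduces.

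**2. Growth needed for progression.** Let B be the week-8 product and s the fraction by which the product shrinks afterwards, so the smallest product is N = (1 - s)B.

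- As written: progression at 1.5B, which is growth from the smallest size of 1.5/(1 - s) - 1.
- Nadir rule: progression at 1.5N, always growth of 50%.

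The documents give no lesion sizes. B = 16 cm² (4 x 4 cm) and the values of s are assumptions.

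| Shrinkage after week 8 | Smallest product (cm²) | Threshold as written (cm²) | Nadir threshold (cm²) | Growth from smallest, as written |
|---|---|---|---|---|
| 0% | 16 | 24 | 24 | +50% |
| 25% | 12 | 24 | 18 | +100% |
| 50% | 8 | 24 | 12 | +200% |
| 75% | 4 | 24 | 6 | +500% |
| 90% | 1.6 | 24 | 2.4 | +1,400% |

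Example: 4 x 4 cm at week 8, 2 x 2 cm at its smallest, then 4.8 x 4.8 cm = 23.04 cm². Against week 8 this is 23.04/16 - 1 = +44%, not progression. Against the smallest product it is 23.04/4 - 1 = +476%.

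**3. Category recorded meanwhile.** Below 16 cm² the lesion is still smaller than at week 8 and fits partial response if there are no new sites. From 16 cm² to just under 24 cm² it is stable disease.

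**4. Disappearance.**

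- Gone after week 8, then back at 3 x 3 cm: 9/16 - 1 = -44%. Not progression.
- Gone at week 8: B = 0, and the percent increase divides by zero. The text gives no answer.

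**5. When the rules can differ.** At 4.345 weeks per month, 5-6 months is weeks 21.7 to 26.1. The nearest scheduled scan is week 20 (4.6 months). The next is about week 20 + 13 = 33 (7.6 months). At week 20 the only earlier post-treatment scan is week 8, so the smallest earlier product is the week-8 product and both percentage rules give the same call, except where that product is zero. They otherwise first differ at about week 33, for lesions smaller at week 20 than at week 8.

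**6. Effect on the trigger, only if late failures count.** Let f be the true failure rate and m the share of failures missed, both assumed. The number seen in 10 patients is binomial with probability f(1 - m). The chance of at least four is:

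| True rate f | m = 0 | m = 10% | m = 25% | m = 50% |
|---|---|---|---|---|
| 30% | 0.350 | 0.273 | 0.169 | 0.050 |
| 40% | 0.618 | 0.513 | 0.350 | 0.121 |
| 50% | 0.828 | 0.734 | 0.553 | 0.224 |

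The documents give no basis for choosing a value of m.

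**The case against.** The strongest reply is that little of consequence moves. The only timed local-control evaluation, at 5-6 months, rests on the week-8 and week-20 scans and is almost untouched. The endpoint is secondary and meant to give preliminary data; the primary endpoint, hepatic toxicity within 3 months, is not involved. The bidimensional definition was a deliberate revision, and the week-8 baseline has a stated reason. A late progression call also prolongs follow-up, so the measurements are kept and can be re-scored. All of this stands, and it limits the weight of the point.

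A nadir rule also has its own error. In the 2 x 2 cm example the threshold is 6 cm², about 2.45 x 2.45 cm, so 4.5 mm per diameter would be called progression and end follow-up. That stands too and is why the fix needs a minimum absolute increase.

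A reader might infer more than the text supports:

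- **That every lesion which shrinks and regrows is scored as controlled.** Regrowth to 1.5 times the week-8 product is progression, and shrinkage before week 8 is already in the baseline. A zero baseline is undefined, not scored as controlled. Nor do the documents ever equate local control with absence of progression.
- **That a two-year local-control rate is overstated.** Section 5.5 sets two years of visits, but 7.1 and 7.3 specify no two-year estimate.
- **That shrinkage followed by regrowth is a usual way to fail.** Nothing in the documents gives its frequency.

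The reply does not remove the rule itself. The stated baseline covers progression as well as response, so a nadir convention cannot be read in, and no other section repairs it.

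**Conclusion.** The point holds for late regrowth below 1.5 times the week-8 product and for lesions absent at week 8. It should be fixed, but it does not threaten the primary endpoint.

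Under the assumed shrinkages of 25 to 90%, progression is called only after growth of 100 to 1,400% from the smallest product, where a nadir rule needs 50%. These figures show what the rule allows, not how often it misclassifies. The effect on the 70% goal and the four-failure trigger is conditional on late failures being counted and on local failure meaning progression under 5.6.1. The plan states neither.

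**What to change.** In 5.6.1:

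1. Define progression of an irradiated lesion as an increase of at least 50% in its diameter product over the smallest product recorded at or after the week-8 scan, together with a minimum absolute increase fixed before re-scoring. Starting at week 8 keeps the reason given for that baseline.
2. State that reappearance of an irradiated lesion that had disappeared, including one absent at week 8, is progression of that irradiated lesion and is not filed under 5.6.2.
3. State that progression takes precedence over partial response, since a regrowing lesion still below its week-8 size would otherwise meet both.
4. State that local failure means progression by this rule.

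Re-score the stored measurements before any local-control figure is reported.

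The cost is a few sentences, a choice of the minimum increase, and the re-scoring. Late local-control figures may become slightly less favourable. Small nadirs are more exposed to measurement error, which the minimum increase limits but does not remove. The minimum would also apply at week 20, so it could withdraw a call that the present rule makes on a very small lesion; scans after follow-up stopped on such a call may not exist.
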